1.2 Rationale for Study

In conclusion, data suggests that treatment of critically ill, non-surgical candidates with EUS-GBD using the AXIOS™ stent results in clinical resolution of their acute cholecystitis coupled with a better quality of life resulting from shorter post-procedural hospital stay, lower post-procedural pain scores, and most notably – fewer post-procedural interventions. We propose a multi-center single arm prospective study in 30 patients to confirm the safety and efficacy of AXIOS™ for EUS-GBD in patients referred to percutaneous drainage of the gallbladder due to advanced age, anesthetic risk, significant co-morbidities and/or overall health.

2 Device Description

Study devices are manufactured by Boston Scientific Corporation. The AXIOS™ Stent is a flexible, fully-covered self-expanding metal stent that is preloaded within the Electrocautery-Enhanced Delivery System. The stent is made of nitinol and fully-covered with silicone. The AXIOS™ Stent and Electrocautery-Enhanced Delivery System is compatible with therapeutic echoendoscopes having a working channel of 3.7mm diameter or larger. The AXIOS™ Stent and Electrocautery-Enhanced Delivery System is intended for single use and is provided sterile using ethylene oxide.

The study device is indicated for use to facilitate drainage of the biliary tract (which includes the gallbladder) outside of the U.S. The study device is not approved for gallbladder drainage in the U.S. and will be considered investigational for this indication. Local Ethics Committee (EC)/Institutional Review Board (IRB)/Research Ethics Board (REB) approval will be obtained at each participating center.

Study devices are labeled on the box and inner pouch and include information not limited to name of legal manufacturer, device name and dimensions, lot number and expiration date. Device labeling will be provided in local language(s) as per national regulations. Devices will be available in the following matrix:

Table 2.0-1: Device Matrix

Description	Stent Size				Delivery System Outer Diam.
	Lumen Diameter	Saddle Length	Overall Stent Length	Flange Diameter	
Electrocautery Enhanced AXIOS™ System with 10x10 Stent	10 mm	10 mm	20 mm	21 mm	10.8Fr
Electrocautery Enhanced AXIOS™ System with 15x10 Stent	15 mm	10 mm	20 mm	24 mm	10.8Fr

For a detailed description of the AXIOS™ Stent and Electrocautery-Enhanced Delivery System, please reference the Investigator's Brochure.

2.1 Device Use

Current cleared indication for use: The AXIOS™ Stent and Electrocautery Enhanced Delivery System is cleared in the US “for use to facilitate transgastric or transduodenal endoscopic drainage of symptomatic pancreatic pseudocysts \geq 6cm in size and walled-off necrosis \geq 6cm in size with \geq 70% fluid content that are adherent to the gastric or bowel wall. Once placed, the AXIOS™ Stent functions as an access port allowing passage of standard and therapeutic endoscopes to facilitate debridement, irrigation and cystoscopy. The stent is intended for implantation up to 60 days and should be removed upon confirmation of

pseudocyst or walled-off necrosis resolution” Outside the U.S., the AXIOS™ Stent and Electrocautery Enhanced Delivery System are indicated for use to facilitate transgastric or transduodenal endoscopic drainage of a pancreatic pseudocyst or walled-off necrosis with \geq 70% fluid content or to facilitate drainage of the biliary tract.

Proposed expanded indication in the U.S. for this IDE study: The AXIOS™ Stent and Electrocautery Enhanced Delivery System is intended for endoscopic ultrasound-guided transluminal gallbladder drainage in patients with acute cholecystitis who are at high risk or unsuitable for surgery.

3 Study Objective

To evaluate the safety and effectiveness of the AXIOS™ Stent with Electrocautery Enhanced Delivery System in the management of symptoms of acute cholecystitis as an alternative to percutaneous gallbladder drainage.

4 Endpoints and Study Design

4.1 Primary Effectiveness Endpoint

The primary effectiveness endpoint is time to resolution of acute cholecystitis which will be measured in days. Resolution is defined as either a fever of less than 100.5°F, or at least a 4-point decrease in the pain score, or WBC count less than 12,000/cc, with improvement in at least two of these categories without the deterioration of the third category.

4.2 Secondary Effectiveness Endpoint

The secondary effectiveness endpoint is the rate of re-interventions including but not limited to stent migration, stent occlusion by GB stones, and luminal debridement.

4.3 Additional Endpoints

[figure not shown]
1. Stent patency (ability to facilitate gallbladder drainage) defined indirectly as resolution of acute cholecystitis or, in the absence of resolution of acute cholecystitis, endoscopic observation of unobstructed AXIOS™ stent lumen
2. Technical stent placement success: Successful stent placement, defined as transmural placement of the AXIOS™ stent with confirmed stent patency via (i) drainage visualized through the stent or fluoroscopically, or (ii) ability to endoscopically observe the inner walls of the gallbladder through the AXIOS™ stent
3. Technical stent removal success: Successful stent removal, defined as ability to remove the AXIOS™ stent endoscopically without stent removal related serious adverse events
4. Rate of recurrence of acute cholecystitis and its management

5. Number of cumulative hospital and ICU days from initial stent placement to resolution of symptoms of acute cholecystitis.

4.4 Study Design

This study is a prospective, multi-center, single arm, consecutive series study. Treatment of up to 30 subjects will take place at up to 9 clinical centers. Subjects who meet all eligibility criteria will receive the AXIOS™ stent for up to 8 weeks stent indwell (unless medically recommended otherwise, i.e. the stent remain indwelling indefinitely) and 30-day follow-up after stent removal.

Figure 4.4-1: AXIOS™ for GB Drainage IDE Study Design

5 Subject Selection

5.1 Inclusion Criteria

Subjects who meet all of the following criteria may be given consideration for inclusion in this clinical investigation, provided no exclusion criterion is met.

1. Patients requiring intervention for the management of symptoms associated with acute cholecystitis
2. Patients referred to percutaneous drainage of the gallbladder who are not surgical candidates because of advanced age, anesthetic risk, significant co-morbidities and/or overall health
3. Eligible for endoscopic intervention
4. Acute Cholecystitis, Grade I (mild) or II (moderate) per Tokyo guidelines [3]:
 - AC Grade I (mild) defined as acute cholecystitis in an otherwise healthy patient with mild local inflammatory changes and without organ dysfunction. Criteria for grade II or III not met.
 - AC Grade II (moderate) defined by any one of the following characteristics
 - Leukocytosis ($>18,000$ cells per mm^3)
 - Palpable, tender mass in right upper quadrant
 - Symptom duration >72 hours
 - Marked local inflammation (gangrenous or emphysematous cholecystitis, pericholecystic or hepatic abscess, biliary peritonitis)
5. Pre-drainage imaging confirms sufficient stone-free space to allow AXIOS™ stent deployment and complete flange expansion
6. 18 years of age or older
7. Willing and able to comply with the study procedures and patient or Legally authorized representative (LAR) must provide written informed consent form (ICF) to participate in the study

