7.4 Visit Schedule

Screening / Baseline – Office/Hospital Visit:

- Informed Consent
- Eligibility Criteria Assessment
- Demographics
- Medical History
- Pre-Procedure imaging within 5 days of drainage procedure (CT scan or transabdominal ultrasound)

Note: If there has been a deterioration of the patient's clinical status or worsening of the patients' liver chemistry profile since the most recent pre-procedure imaging, then additional imaging is needed to evaluate if the patient is still a candidate for the intervention.

- Current Medications
- Pre-Procedure subject management including labs and clinical symptom assessment
 - Laboratory markers of inflammation or cholestasis
 - White Blood Cells (WBC)
 - Hemoglobin
 - Alanine aminotransferase

- Alkaline phosphatase
- C reactive protein
- Bilirubin

Stent Placement Procedure – Office/Hospital Visit

- Stent Placement
- Imaging (as applicable)
- Adverse Events Assessment / Device Event Assessment
- Stent Patency Assessment
- Current Medications

Note: See DFU/ IB and Additional Procedural Notices below for procedure guidance.

Additional Procedural Notices:

- *Procedure should be done with CO₂ insufflation.*
- *Choice of placement of stent between the duodenum and the gallbladder or between the stomach and the gallbladder is left at discretion of treating physician.*
- *Physicians will select the site of the AXIOS™ stent placement under EUS guidance and choose an access location where there is*
 - *adequate stone-free space within the gallbladder to deploy the flange*
 - *distance between the gallbladder and the stomach or duodenal lumen that does not exceed 10mm, the saddle length of the AXIOS™ stent*
 - *no intervening ascites, bowel, or fat, as identified by EUS*
- *If a patient's gallbladder has minimal stone burden and is free of large stones per baseline imaging, a 10mm lumen diameter AXIOS™ stent is recommended*
- *If a patient's gallbladder is packed with stones or large stones (1cm or larger in diameter) are present per baseline imaging, a 15mm lumen diameter AXIOS™ stent is recommended*
- *Stones and/or sludge will be cleared using gentle basketing and irrigation through the stent if necessary, at the discretion of investigator*
- *Placement of double pigtail plastic stent(s) through AXIOS™ will not be allowed in the study.*

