3.1.3 Analysis

The primary effectiveness endpoint will be evaluated for all ITT patients regardless of whether an AXIOS™ stent is implanted. Patients for whom an AXIOS™ stent is implanted and cholecystitis is resolved will be considered a success for the endpoint and the days to resolution will be the date of resolution minus the date of the index procedure. If a patient does not receive an AXIOS™ stent, the patient will be considered a failure for the endpoint with censoring at 60 days. If a subject receiving an AXIOS™ stent does not achieve resolution of cholecystitis for any reason, the patient will be treated as censored in the Kaplan-Meier analysis and the days to censoring will be the date of censoring minus the date of the index procedure. The date of censoring will be the earliest of the following:

- date of the patient receiving a cholecystectomy,
- date of the patient dying,
- date of last contact for patients who withdraw from the study or are lost to follow-up, or
- date of the AXIOS™ stent removal.

The mean time to resolution and standard error of the mean will be estimated from a Kaplan-Meier analysis so that subjects for whom resolution is not obtained can be included in the analysis.

The estimated mean, $\hat{\mu}_T$, from the Kaplan-Meier analysis will be calculated as:

$$\hat{\mu}_T = \int_0^T \hat{S}(t)dt$$

where $\hat{S}(t)$ is the estimated survival function from the Kaplan-Meier analysis and T is time of longest days to resolution or days to censoring. The variance of $\hat{\mu}_T$, $\hat{V}(\hat{\mu}_T)$, is estimated as:

$$\hat{V}(\hat{\mu}_T) = \sum_{i=1}^D \left[\int_{t_i}^T \hat{S}(t)dt \right]^2 \frac{d_i}{Y_i(Y_i - d_i)}$$

where D is the number of distinct times (days to resolution), t_i is the i-th time, Y_i is the number of patients at risk at time t_i , and d_i is the number of events at time t_i . The $100(1 - \alpha)\%$ upper bound of the confidence interval of the mean will be calculated as:

$$\hat{\mu}_T + Z_{1-\alpha} \sqrt{\hat{V}(\hat{\mu}_T)}$$

For the primary effectiveness endpoint of days to clinical resolution, testing will be performed as described below.

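### The clock starts at the stent procedure, but the readings that define resolution need not be taken near it, so improvement before the stent can be scored as a 0-1 day resolution.

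*Protocol*

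**What the plan says.** **Time zero.** SAP 3.1.3 states that "the days to resolution will be the date of resolution minus the date of the index procedure", and protocol 8.1 uses the same rule.

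**Resolution.** Protocol 4.1 and SAP 3.1 name three criteria: "either a fever of less than 100.5°F, or at least a 4-point decrease in the pain score, or WBC count less than 12,000/cc". A patient counts as resolved when two or more of the three have improved and the remaining one has not worsened. Neither section says which earlier reading improvement or deterioration is measured from.

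**When the readings are taken.** Protocol 7.1 and 7.4 list the clinical symptom assessment and labs at screening/baseline, then at the daily visits after placement. The stent placement visit lists neither. The only window at baseline is for imaging: "Pre-Procedure imaging within 5 days of drainage procedure (CT scan or transabdominal ultrasound"). The only re-check before the procedure in 7.4 is repeat imaging, triggered by deterioration. Protocol 7.5 asks for average pain since the prior visit.

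**Entry.** Inclusion criterion 1 reads "Patients requiring intervention for the management of symptoms associated with acute cholecystitis". For severity, "AC Grade I (mild) defined as acute cholecystitis in an otherwise healthy patient with mild local inflammatory changes and without organ dysfunction" carries no temperature, WBC or pain value. "AC Grade II (moderate) defined by any one of the following characteristics" is followed by four alternatives. WBC above 18,000 is one of them, and symptom duration over 72 hours suffices alone.

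**The concern.** Improvement before the stent is foreseeable. Protocol 1.1 describes timely antibiotics as part of treatment, and 7.1 records antibiotics and pain medication at baseline. Consider a patient screened at 101.5°F, WBC 15,000 and pain 8 who is at 99°F, 11,000 and pain 4 on the morning of the procedure. Measured from screening, all three categories have improved and the definition is met before the device is in place. The first listed reading after that is post-stent, so the data would show a resolution at day 0 or 1 and could not show when the change happened.

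The trial has no control arm in which the same early improvement would also appear. The planned margin is only 1.15 days (3.5 minus 2.35), so a modest number of such scores could carry the primary claim.

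**Working it through.** **1. The plan's own figure.** Inputs from SAP 3.1.2: mean 2.35, goal 3.5, SD 2, n = 27, one-sided alpha 0.025. One-sample t-test, noncentrality (1.15/2) × √27 = 2.99, gives power 82.0% against the stated 82%. At the protocol's alpha of 0.022 it gives 80.4%, as stated. Enrolment is 27/0.9 = 30. The arithmetic is sound; the issue is how the endpoint is measured.

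**2. Effect on the mean.** Let a share f already meet the definition at the procedure and score day t0 (0 or 1), while the others average M. The observed mean is M(1 − f) + t0·f. With M = 3.5 (no advantage over the goal):

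| f | scored day 0 | scored day 1 |
|---|---|---|
| 10% | 3.15 | 3.25 |
| 20% | 2.80 | 3.00 |
| one third | 2.33 | 2.67 |

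The whole planned effect would appear without device benefit at f = 1.15/3.5 = 33% (day 0) or 1.15/2.5 = 46% (day 1). Starting from the cited percutaneous mean of 4.6 days, reaching the goal takes f = 1.1/4.6 = 24% or 1.1/3.6 = 31%.

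**3. Effect on the test.** Simulation with n = 30, gamma-distributed times with SD 2, the SAP Kaplan-Meier mean and its z-based 97.5% upper bound. Chance of declaring primary success:

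| Assumption for the other patients | f = 0 | 10% | 20% | one third |
|---|---|---|---|---|
| mean 3.5, no placement failure, day 0 | about 5% | 19% | 43-44% | 75-77% |
| mean 3.5, no placement failure, day 1 | about 5% | 16% | 33% | 63% |
| mean 3.5, 4.5% placement failures, day 0 | about 1% | 5-6% | 10-11% | 19% |
| mean 4.6, no placement failure, day 0 | about 0% | about 0% | 1-2% | 17% |

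The excess over 2.5% at f = 0 in the first two rows comes from the z-based bound in a small skewed sample and is not part of this point.

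The third row uses Appendix 24.1 technical success, 252/264, so 12/264 = 4.5% failures, each censored at day 60 under SAP 3.1.3. One such patient adds about 60/30 = 2 days to the mean, so success then essentially requires no failure at all. That has probability (252/264)^30 = 25%, and 0.25 × 44% = 11%, in line with the table.

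**4. A remedy that would backfire.** Suppose only categories abnormal at the reference reading could count as improved. A patient with no abnormal category could then never resolve and would be censored, typically at stent removal (planned for days 30-60). Take one such patient in 30, censored at day 30, and the other 29 at the planned mean of 2.35 and SD 2:

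- mean = (29 × 2.35 + 30)/30 = 3.27
- variance = (29/30) × 4 + (29/900) × 27.65² = 28.5, so SE = √(28.5/30) = 0.975
- upper bound = 3.27 + 1.96 × 0.975 = 5.18, far above 3.5

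In simulation the bound averaged about 5.2 and the test failed in all 3,000 runs.

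**The case against.** **The bias might seem to hold however improvement is read.** It does not. Take a patient who is never febrile and has WBC 10,000 at entry. If being below the thresholds is enough, this patient is inside two of the three from the start. If real change is required, the patient cannot improve in two categories, never resolves, and lengthens the mean. Only the patient who was abnormal at screening and improved before the stent is favoured on both readings.

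**Entry might seem to need no abnormal value at all.** The documents support only that no threshold is printed. Patients must need intervention and be referred for percutaneous drainage, and the cited grading source may carry diagnostic criteria that are not reproduced.

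**Early improvement is hypothetical.** Baseline readings could be same-day, and the 5-day window concerns imaging. This stands as far as it goes: improvement before the stent can be credited to it, and nothing shows that it is. But nothing in the schedule prevents it or would detect it.

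**The plan has opposing features.** Censoring at day 60 for failed placement cuts the success rates to roughly a quarter, and the goal already lies 1.1 days below the cited 4.6. Both stand, and the range above reflects them. They offset the bias without removing it: with placement failures, success still rises from about 1% to 10-11% at f = 20%.

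**The percutaneous series may contain early improvers too.** The documents do not say how time zero was set there, so an offset can be neither shown nor assumed.

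**Conclusion.** The point holds as a gap in measurement. Time zero is fixed at the procedure, the readings behind the endpoint are not tied to it, and the reference for improvement is unnamed. Any resulting credit for improvement before the stent favours the device.

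Its size cannot be settled from the documents, because f is assumed throughout. At f = 10-20%, the chance of primary success without a true advantage over the goal runs from 16% to 44% if the others average 3.5 days and no placement fails, and from about 5% to 11% with 4.5% failures. If the others average 4.6 days it is at most about 2%. The highest figures (63-77% at one third) need both a large f and no placement failure, so they should not be read as expected error rates. The stated sample size and power are unaffected.

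**What to change.** 1. In protocol 7.1 and 7.4, require the baseline pain score, temperature and WBC already collected to be taken and dated within 24 hours before the index procedure. In protocol 4.1 and SAP 3.1, name those values as the only reference for improvement and deterioration.
2. In the SAP, tabulate patients who at that reading are already below the temperature and WBC thresholds, or who have already met the definition relative to an earlier screening reading. Repeat the primary test without them as a pre-specified sensitivity analysis.
3. Do not add a rule that only categories abnormal at that reading can improve unless the SAP also says how patients with no abnormal category are scored. Otherwise one such patient can make the primary test fail.

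**Cost.** A short protocol amendment with its approvals (the amendment log shows that the primary endpoint has been revised after regulatory feedback before), SAP wording and one extra analysis. The readings must fall within 24 hours of the procedure, which will occasionally mean repeating a blood count. The estimated mean time to resolution may come out somewhat longer.

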5.2 Exclusion Criteria

Subjects who meet any one of the following criteria will be excluded from this clinical study.

1. AC Grade III (severe) per Tokyo guidelines [3] defined by organ dysfunction in any one of the following systems:
 - Cardiovascular - Hypotension requiring administration of $\geq 5\mu\text{g}/\text{kg}/\text{min}$ of dopamine or any dose of norepinephrine
 - Neurologic - Decreased level of consciousness
 - Respiratory - $\text{PaO}_2/\text{FiO}_2 < 300$
 - Renal - Oliguria and Creatinine > 2.0 mg/dl (> 177 $\mu\text{mol}/\text{liter}$)
 - Hepatic - International normalized ratio > 1.5
 - Hematologic - Platelet count $< 100,000/\text{mm}^3$

2. Obvious signs on diagnostic imaging of perforated, extensive gangrenous or ischemic gallbladder [44, 45]
3. Hepatic abscess
4. Ascites
5. Patients with abnormal coagulation or who require ongoing complete anticoagulation
6. Bleeding diathesis
7. History of surgical treatment of acute cholecystitis (e.g. cholecystectomy)
8. Patients with a current percutaneous drainage
9. Patients with a history of percutaneous gallbladder drainage without AC free period following percutaneous drainage removal
10. Distance between gallbladder wall and duodenal or gastric wall > 1cm by US (ultrasound) at the time of drainage
11. Patients with intervening gastric varices or vessels within a one centimeter radius of the device insertion location
12. Patients that have allergies or are sensitive to any of the device materials
13. Patients with contraindications to use of electrical devices
14. Pregnancy
15. Prisoners and other vulnerable populations

6 Subject Accountability

6.1 Point of Enrollment

A subject is considered “enrolled” after signing the study-specific Informed Consent Form (ICF). Subjects who sign the ICF but subsequently do not meet one or more of the selection criteria will be considered screen failures and excluded from the study.

6.2 Withdrawal

All subjects enrolled in the clinical study (including those withdrawn from the clinical study or lost to follow-up) shall be accounted for and documented. If a subject withdraws from the clinical investigation, the reason(s) shall be reported. If such withdrawal is due to problems related to investigational device safety or performance, the investigator shall ask for the subject’s permission to follow his/her status/condition outside of the clinical study.

Reasons for withdrawal include physician discretion, subject choice to withdraw consent, loss to follow-up, and death. While study withdrawal is discouraged, subjects may withdraw from the study at any time, with or without reason, and without prejudice to further treatment.

All applicable case report forms up to the point of subject withdrawal must be completed. Additional data may no longer be collected after the point at which a subject has been withdrawn from the study or withdraws his/her consent, for whatever reason. All open adverse events should be closed or include resolution status. Data collected up to the point of subject withdrawal may be used. Withdrawn subjects will not be replaced. Subjects who withdraw from the study with the study stent in place will be followed per standard of care at the local institution.

6.3 *Lost to Follow-Up*

A subject will be considered lost to follow-up if the subject remains unresponsive to communication after three documented attempts by study staff. (where possible, 3 telephone calls and, if necessary, a certified letter to the subject's last known mailing address or local equivalent methods).

However, for those subjects who remain unresponsive to communication while the stent remains in place, additional attempts will be made to request the subject's return for study stent removal. These additional attempts may include increased telephone and written communications and contact with the subject's primary care physician (if this communication is consented to in the Informed Consent Form). These contact attempts should be documented in the subject's medical record or study file.

Should the subject continue to be unreachable, he or she will be considered to have withdrawn from the study with a primary reason of lost to follow-up.

6.4 *Subject Status and Classification*

Enrolled Cohort

A subject will be considered enrolled when the ICF is signed.

Intent-to-treat Cohort

The intent-to-treat (ITT) cohort is defined as all subjects who signed the ICF, were evaluated for inclusion/exclusion criteria, and in whom the endoscopic procedure was initiated. Subjects in the ITT cohort will be counted towards the enrollment ceiling and this cohort will be considered the primary analysis cohort.

Treated Cohort

The treated cohort is defined as all ITT subjects who have an AXIOS™ stent implanted for the purpose of gallbladder drainage.

Per Protocol Cohort

The per-protocol cohort is defined as all treated subjects for whom an AXIOS™ stent was implanted for the purpose of gallbladder drainage and met all eligibility criteria.

6.5 *End of Study Definition*

A clinical trial is considered completed when ***subjects*** are no longer being examined or the last ***subject***'s last study visit has occurred.

7 Study Methods

